## 5.2 Trial Treatments

The treatment to be used in this trial is outlined below in **Table 2**

**Table 2. Trial Treatment**

Drug	Dose/Potency	Dose Frequency	Route of Administration	Regimen/ Treatment Period	Use
Pembrolizumab	200 mg	Q3W	IV infusion	Day 1 of each 3 week cycle	Experimental

### 5.2.1 Dose Selection/Modification

#### 5.2.1.1 Dose Selection

The rationale for selection of doses to be used in this trial is provided in Section 4.0 – Background & Rationale.

#### 5.2.1.2 Dose Modification and toxicity management for immune-related AEs associated with pembrolizumab and combination therapy

Adverse events (both non-serious and serious) associated with pembrolizumab exposure, including coadministration with additional compounds, may represent an immunologic etiology. These adverse events may occur shortly after the first dose or several months after the last dose of treatment and may affect more than one body system simultaneously. Therefore, early recognition and initiation of treatment is critical to reduce complications. Based on existing clinical study data, most irAEs were reversible and could be managed with interruptions of pembrolizumab/combination treatment, administration of corticosteroids and/or other supportive care. For suspected irAEs, ensure adequate evaluation to confirm etiology or exclude other causes. Additional procedures or tests such as bronchoscopy, endoscopy, skin biopsy may be included as part of the evaluation. Dose modification and toxicity management guidelines for irAEs associated with pembrolizumab/combination treatment are provided in Table 3 below.

**Table 3. Dose Modification Guidelines for Drug-Related Adverse Events**

Toxicity	Hold Treatment For Grade	Timing for Restarting Treatment	Discontinue Subject
Diarrhea/ Colitis	2-3	Toxicity resolves to Grade 0-1.	Toxicity does not resolve within 12 weeks of last dose or inability to reduce corticosteroid to 10 mg or less of prednisone or equivalent per day within 12 weeks.
	4	Permanently discontinue	Permanently discontinue
AST, ALT, or Increased Bilirubin	2	Toxicity resolves to Grade 0-1	Toxicity does not resolve within 12 weeks of last dose.
	3-4	Permanently discontinue (see exception below) 	Permanently discontinue
Type 1 diabetes mellitus (if new onset) or Hyperglycemia	T1DM or 3-4	Hold pembrolizumab for new onset Type 1 diabetes mellitus or Grade 3-4 hyperglycemia associated with evidence of beta cell failure.	Resume pembrolizumab when patients are clinically and metabolically stable.
Hypophysitis	2-3	Toxicity resolves to Grade 0-1	Toxicity does not resolve within 12 weeks of last dose or inability to reduce corticosteroid to 10 mg or less of prednisone or equivalent per day within 12 weeks.
	4	Permanently discontinue	Permanently discontinue
Hyperthyroidism	3	Toxicity resolves to Grade 0-1	Toxicity does not resolve within 12 weeks of last dose or inability to reduce corticosteroid to 10 mg or less of prednisone or equivalent per day within 12 weeks.
	4	Permanently discontinue	Permanently discontinue
Hypothyroidism	2-4	Therapy with pembrolizumab can be continued while treatment for the thyroid disorder is instituted	Therapy with pembrolizumab can be continued while treatment for the thyroid disorder is instituted.
Infusion Reaction	3-4	Permanently discontinue	Permanently discontinue
Pneumonitis	2	Toxicity resolves to Grade 0-1	Toxicity does not resolve within 12 weeks of last dose or inability to reduce corticosteroid to 10 mg or less of prednisone or equivalent per day within 12 weeks.
	3-4	Permanently discontinue	Permanently discontinue
Renal Failure or Nephritis	2	Toxicity resolves to Grade 0-1	Toxicity does not resolve within 12 weeks of last dose or inability to reduce corticosteroid to 10 mg or less of prednisone or equivalent per day within 12 weeks.
	3-4	Permanently discontinue	Permanently discontinue

Toxicity	Hold Treatment For Grade	Timing for Restarting Treatment	Discontinue Subject
All Other Drug-Related Toxicity 	3 or Severe	Toxicity resolves to Grade 0-1	Toxicity does not resolve within 12 weeks of last dose or inability to reduce corticosteroid to 10 mg or less of prednisone or equivalent per day within 12 weeks.
	4	Permanently discontinue	Permanently discontinue

**Note: Permanently discontinue for any severe or Grade 3 drug-related AE that recurs or any life-threatening event.**

 For patients with liver metastasis who begin treatment with Grade 2 AST or ALT, if AST or ALT increases by greater than or equal to 50% relative to baseline patients should hold therapy and have imaging to assess for progression. If no progression is seen and abnormalities persist for at least 1 week then patients should be discontinued.

 Patients with intolerable or persistent Grade 2 drug-related AE may hold study medication at physician discretion. Permanently discontinue study drug for persistent Grade 2 adverse reactions for which treatment with study drug has been held, that do not recover to Grade 0-1 within 12 weeks of the last dose.

Dosing interruptions are permitted in the case of medical / surgical events or logistical reasons not related to study therapy (e.g., elective surgery, unrelated medical events, patient vacation, and/or holidays). Subjects should be placed back on study therapy within 3 weeks of the scheduled interruption, unless otherwise discussed with the Sponsor. The reason for interruption should be documented in the patient's study record.

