**Grade 2 hyperthyroidism events (and Grade 2-4 hypothyroidism):**

In hyperthyroidism, non-selective beta-blockers (e.g. propranolol) are suggested as initial therapy.

In hypothyroidism, thyroid hormone replacement therapy, with levothyroxine or liothyronine, is indicated per standard of care.

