#### 5.6 Subject Withdrawal/Discontinuation Criteria

Subjects may withdraw consent at any time for any reason or be discontinued from the trial at the discretion of the investigator should any untoward effect occur. In addition, a subject may be withdrawn by the investigator or the Sponsor if enrollment into the trial is inappropriate, the trial plan is violated, or for administrative and/or other safety reasons. Specific details regarding discontinuation or withdrawal are provided in Section 7.1.4.

A subject must be discontinued from the trial for any of the following reasons:

- The subject or legal representative (such as a parent or legal guardian) withdraws consent.
- Confirmed radiographic disease progression  
*Note:* For unconfirmed radiographic disease progression, please see Section 7.1.2.5.4 A subject may be granted an exception to continue on treatment with confirmed radiographic progression if clinically stable or clinically improved.
- Unacceptable adverse experiences as described in Section 5.2.1.2
- Intercurrent illness that prevents further administration of treatment
- Investigator's decision to withdraw the subject
- The subject has a confirmed positive serum pregnancy test
- Noncompliance with trial treatment or procedure requirements
- The subject is lost to follow-up
- Completed 24 months of uninterrupted treatment with pembrolizumab or 35 administrations of study medication, whichever is later.

*Note: 24 months of study medication is calculated from the date of first dose. Subjects who stop pembrolizumab after 24 months may be eligible for up to one year of additional study treatment if they progress after stopping study treatment provided they meet the requirements detailed in Section 7.1.5.5*

RUTGERS | eIRB  
APPROVED

IRB ID: Pro20170001392  
Approval Date: 2/22/2023  
Expiration Date: 5/10/2023

- Administrative reasons

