**Table 6. Evaluating Adverse Events**

An investigator who is a qualified physician, will evaluate all adverse events as to:

V4.0 CTCAE Grading	Grade 1	Mild; asymptomatic or mild symptoms; clinical or diagnostic observations only; intervention not indicated.
	Grade 2	Moderate; minimal, local or noninvasive intervention indicated; limiting age-appropriate instrumental ADL.
	Grade 3	Severe or medically significant but not immediately life-threatening; hospitalization or prolongation of hospitalization indicated; disabling; limiting self-care ADL.
	Grade 4	Life threatening consequences; urgent intervention indicated.
	Grade 5	Death related to AE
Seriousness	A serious adverse event is any adverse event occurring at any dose or during any use of Merck product that:	
	† Results in death ; or	
	† Is life threatening ; or places the subject, in the view of the investigator, at immediate risk of death from the event as it occurred (Note: This does not include an adverse event that, had it occurred in a more severe form, might have caused death.); or	
	† Results in a persistent or significant disability/incapacity (substantial disruption of one's ability to conduct normal life functions); or	
	† Results in or prolongs an existing inpatient hospitalization (hospitalization is defined as an inpatient admission, regardless of length of stay, even if the hospitalization is a precautionary measure for continued observation. (Note: Hospitalization [including hospitalization for an elective procedure] for a preexisting condition which has not worsened does not constitute a serious adverse event.); or	
	† Is a congenital anomaly/birth defect (in offspring of subject taking the product regardless of time to diagnosis); or	
	Is a new cancer ; (that is not a condition of the study) or	
	Is an overdose (whether accidental or intentional). Any adverse event associated with an overdose is considered a serious adverse event. An overdose that is not associated with an adverse event is considered a non-serious event of clinical interest and must be reported within 24 hours.	

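### The note under Table 3 and two of its rows (hypothyroidism; new-onset type 1 diabetes or hyperglycemia with beta cell failure) conflict when the event is life-threatening

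*Combined protocol and SAP*

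**What the plan says.** Section 5.2.1.2 sets the dose-modification rules in Table 3, with a bold note directly beneath it: "Permanently discontinue for any severe or Grade 3 drug-related AE that recurs or any life-threatening event".

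Two rows of the table bear on this.

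- **Hypothyroidism, Grades 2 to 4.** The restart column and the Discontinue Subject column carry the same sentence: "Therapy with pembrolizumab can be continued while treatment for the thyroid disorder is instituted".
- **New-onset type 1 diabetes or Grade 3-4 hyperglycemia.** The restart column says: "Hold pembrolizumab for new onset Type 1 diabetes mellitus or Grade 3-4 hyperglycemia associated with evidence of beta cell failure". The Discontinue Subject column says: "Resume pembrolizumab when patients are clinically and metabolically stable".

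Table 6 (Section 7.2.4) describes CTCAE Grade 4 as "Life threatening consequences; urgent intervention indicated", and Table 4 also describes a Grade 4 infusion reaction as life-threatening. Table 6 separately lists life-threatening as a seriousness criterion, judged by whether the investigator considers the subject at immediate risk of death from the event as it happened.

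Section 5.6 lists among its mandatory reasons for discontinuation: "Unacceptable adverse experiences as described in Section 5.2.1.2".

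**The concern.** An investigator whose patient has a life-threatening event in either row finds two instructions on one table. The row leads to continuing treatment, or to holding and then resuming it. The note leads to stopping for good. Neither refers to the other.

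Two things are at stake. The first is safety: the protocol should give one answer on whether a patient is re-exposed after a life-threatening event. The second is consistency. Section 10.7 names more than one institution, and if they read the table differently, patients with the same event will have different treatment durations and discontinuation reasons. The reading chosen could also affect retreatment, because one route into the Second Course Phase (Section 7.1.5.5) requires that treatment was not stopped for intolerability.

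**Working it through.** No arithmetic applies beyond a count of rows, so the check is a comparison of texts.

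**Step 1. Grade 4 instruction in each of the ten rows of Table 3.**

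| Row | Grade 4 instruction | Agrees with the note? |
|---|---|---|
| Diarrhea/colitis | Permanent stop | Yes |
| AST, ALT or bilirubin | Permanent stop, with a marked exception (footnote 1) | Yes, apart from the exception |
| New-onset type 1 diabetes or hyperglycemia | Hold, then resume when stable | No, if the event is life-threatening |
| Hypophysitis | Permanent stop | Yes |
| Hyperthyroidism | Permanent stop | Yes |
| Hypothyroidism | Continue | No, if the event is life-threatening |
| Infusion reaction | Permanent stop | Yes |
| Pneumonitis | Permanent stop | Yes |
| Renal failure or nephritis | Permanent stop | Yes |
| All other drug-related toxicity | Permanent stop | Yes |

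Eight rows agree with the note and two do not (10 - 8 = 2).

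**Step 2. Is there a stated exception or order of precedence?** None was found.

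- Footnote 1 concerns AST or ALT in patients with liver metastasis. Footnote 2 concerns Grade 2 events under other toxicity. Neither touches the two rows.
- Where an exception was intended, the table flags it: the AST/ALT/bilirubin row points to its footnote. The two rows in question carry no such flag.
- A general exemption for endocrine events cannot be inferred, because Grade 4 hyperthyroidism and Grade 4 hypophysitis are permanent stops.
- The supportive-care text in Section 5.4.1 groups the thyroid events under "Grade 2 hyperthyroidism events (and Grade 2-4 hypothyroidism" and describes treatment of the disorder. It gives no rule on stopping pembrolizumab. Its diabetes text gives none either.
- Section 5.6 refers back to Section 5.2.1.2 and so imports the conflict.
- The rechallenge entry of Table 6 requires advance approval by the clinical monitor for certain re-exposures, but ties that approval to the protocol's own dose-modification guidelines, which are the texts in conflict.

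**Step 3. Which events are caught by the life-threatening clause?** If the note means CTCAE Grade 4, every Grade 4 event covered by the two rows is caught. If it means the seriousness criterion, only those events that put the subject at immediate risk of death are caught. Under both readings some events in these rows are caught.

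**Step 4. Which events are caught by the recurrence clause?** In the diabetes/hyperglycemia row, treatment is held and resumed, so a drug-related Grade 3 hyperglycemia with beta cell failure can return after resumption. The row would again allow resumption; the note would require a permanent stop. In the hypothyroidism row treatment is never interrupted, and the documents do not say what recurrence would mean there, so this branch is not shown for that row.

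**Step 5. Column placement.** In the diabetes row the hold instruction stands under the restart heading, and the resume instruction under Discontinue Subject. The row has four cells for four columns, so this does not look like an artefact of text extraction.

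**The case against.** The best counter-argument is that a specific row governs its named toxicity and the note is a general backstop. The separate grouping of Grade 2-4 hypothyroidism in Section 5.4.1 suggests deliberate handling. This is a plausible reading of intent, but the protocol does not state it, the note admits no exceptions, and the one row with an exception says so.

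A second objection concerns scope, and it stands. A reader might infer that every Grade 4 event in these rows is in conflict. The documents do not establish that: Section 7.2.4 requires seriousness to be assessed whatever the grade, and the note speaks of life-threatening events where the rows use grade numbers. A reader might also extend the conflict to all Grade 4 hyperglycemia. The hold instruction is limited to cases with evidence of beta cell failure, so no conflict is shown outside them. Nor is a recurrent Grade 3 conflict shown for hypothyroidism.

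Third, advance approval of rechallenge makes it less likely that a site resumes treatment on its own reading. That has some force for the diabetes row. It does not say which text prevails, and it does not clearly reach hypothyroidism, where dosing is not interrupted.

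Finally, the column placement is a layout point. Read across, the diabetes row can be understood, and the conflict does not depend on it.

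**Conclusion.** This is an internal inconsistency in a safety rule, and it should be corrected. It affects two of the ten rows of Table 3. It holds for life-threatening hypothyroidism; for life-threatening new-onset type 1 diabetes or hyperglycemia with evidence of beta cell failure; and for a drug-related Grade 3 event that recurs in the diabetes/hyperglycemia row. Whether it extends to every Grade 4 event covered by the rows depends on a definition that the note does not give.

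The conclusion assumes that the note applies to the whole table, as its position and wording indicate. The documents give no frequency for these events. With 40 planned subjects (Section 1.0), few patients may be affected, and no effect on the primary response rate is shown. The reason to act is that Section 5.6 makes discontinuation mandatory by reference to text with two opposite readings.

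**What to change.** The sponsor must reconcile the hypothyroidism and diabetes/hyperglycemia rows with the note to Table 3. The revised text should:

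1. state whether the row or the note governs for these two toxicities, for both the life-threatening and the recurrence clauses;
2. state whether life-threatening in the note means CTCAE Grade 4 or the seriousness criterion in Table 6;
3. put the hold and resume instructions of the diabetes row under the columns to which they belong.

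No view is taken on which clinical rule is right. The cost is about one sentence in the note and a table cell or two, made through a protocol amendment. No sample size, endpoint or analysis changes.

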## 5.2.2 Timing of Dose Administration

Trial treatment should be administered on Day 1 of each cycle after all procedures/assessments have been completed as detailed on the Trial Flow Chart (Section 6.0). Trial treatment may be administered up to 3 days before or after the scheduled Day 1 of each cycle. Patients may be seen separately for physical exam and treatment evaluations if needed no more than 48 hours apart, and a repeat toxicity assessment by study staff must occur on day of treatment. Pembrolizumab 200 mg will be administered as a 30 minute IV infusion every 3 weeks. Sites should make every effort to target infusion timing to be as close to 30 minutes as possible. However, given the variability of infusion pumps from site to site, a window of -5 minutes and +10 minutes is permitted (i.e., infusion time is 30 minutes: -5 min/+10 min).

## 5.2.3 Trial Blinding/Masking

This is an open-label trial; therefore, the Sponsor, investigator and subject will know the treatment administered.

## 5.3 Concomitant Medications/Vaccinations (allowed & prohibited)

Medications or vaccinations specifically prohibited in the exclusion criteria are not allowed during the ongoing trial. If there is a clinical indication for one of these or other medications

or vaccinations specifically prohibited during the trial, discontinuation from trial therapy or vaccination may be required. The investigator should discuss any questions regarding this with the Merck Clinical team. The final decision on any supportive therapy or vaccination rests with the investigator and/or the subject's primary physician.

### 5.3.1 Acceptable Concomitant Medications

All treatments that the investigator considers necessary for a subject's welfare may be administered at the discretion of the investigator in keeping with the community standards of medical care. All concomitant medication will be recorded on the case report form (CRF) including all prescription, over-the-counter (OTC), herbal supplements, and IV medications and fluids. If changes occur during the trial period, documentation of drug dosage, frequency, route, and date may also be included on the CRF.

All concomitant medications received within 28 days before the first dose of trial treatment and 30 days after the last dose of trial treatment should be recorded. Concomitant medications administered after 30 days after the last dose of trial treatment should be recorded for SAEs and ECI as defined in Section 7.2.

### 5.3.2 Prohibited Concomitant Medications

Subjects are prohibited from receiving the following therapies during the Screening and Treatment Phase (including retreatment for post-complete response relapse) of this trial:

- Antineoplastic systemic chemotherapy or biological therapy
- Immunotherapy not specified in this protocol
- Chemotherapy not specified in this protocol
- Investigational agents other than pembrolizumab
- Radiation therapy
  - Note: Radiation therapy to a symptomatic solitary lesion or to the brain may be allowed at the investigator's discretion.
- Live vaccines within 30 days prior to the first dose of trial treatment and while participating in the trial. Examples of live vaccines include, but are not limited to, the following: measles, mumps, rubella, varicella/zoster, yellow fever, rabies, BCG, and typhoid vaccine. Seasonal influenza vaccines for injection are generally killed virus vaccines and are allowed; however, intranasal influenza vaccines (eg, FluMist®) are live attenuated vaccines and are not allowed.
- Systemic glucocorticoids for any purpose other than to modulate symptoms from an event of clinical interest of suspected immunologic etiology. The use of physiologic doses of corticosteroids may be approved after consultation with the Sponsor.

Subjects who, in the assessment by the investigator, require the use of any of the aforementioned treatments for clinical management should be removed from the trial. Subjects may receive other medications that the investigator deems to be medically necessary.

The Exclusion Criteria describes other medications which are prohibited in this trial.

There are no prohibited therapies during the Post-Treatment Follow-up Phase.

## 5.4 Rescue Medications & Supportive Care

### 5.4.1 Supportive Care Guidelines

Subjects should receive appropriate supportive care measures as deemed necessary by the treating investigator. Suggested supportive care measures for the management of adverse events with potential immunologic etiology are outlined below and in Section 5.2.1.2, Table 3. Where appropriate, these guidelines include the use of oral or intravenous treatment with corticosteroids as well as additional anti-inflammatory agents if symptoms do not improve with administration of corticosteroids. Note that several courses of steroid tapering may be necessary as symptoms may worsen when the steroid dose is decreased. For each disorder, attempts should be made to rule out other causes such as metastatic disease or bacterial or viral infection, which might require additional supportive care. The treatment guidelines are intended to be applied when the investigator determines the events to be related to pembrolizumab.

Note: if after the evaluation the event is determined not to be related to pembrolizumab, the Investigator does not need to follow the treatment guidance. Refer to the details below and Section 5.2.1 for dose modification and supportive care.

It may be necessary to perform conditional procedures such as bronchoscopy, endoscopy, or skin photography as part of evaluation of the event.

#### **Pneumonitis:**

For **Grade 2 events**, treat with systemic corticosteroids. When symptoms improve to Grade 1 or less, steroid taper should be started and continued over no less than 4 weeks.

For **Grade 3-4 events**, immediately treat with intravenous steroids. Administer additional anti-inflammatory measures, as needed.

Add prophylactic antibiotics for opportunistic infections in the case of prolonged steroid administration.

